9.3 Visits and Assessments

During each clinic visit all subjects will undergo careful evaluations (by a physician) that will include: medical history such as appearance of any new health problems, any new symptoms/adverse events, introduction of new medication(s) between clinic visits, concomitant medication(s) {medication reconciliation}, physical examination with assessment of vital signs, ASRS, IRLS, RLS-QOL, and MOS-SS.

10. EFFICACY ASSESSMENTS

10.1 Clinical Efficacy Assessments include documenting ASRS, IRLS, RLS-QOL and MOS-SS each visit.

10.2 Safety and Tilerability Assessments

The safety and tolerability of Horizant will be determined by the occurrence of and/or Changes in:

- Treatment-emergent adverse events
- Any clinically significant changes in laboratory tests

• Any new complaints or significant changes in physical examination

Patients will be enquired about adverse effects during each visit.

Labs will be performed as per study design and as needed by investigator's discretion during the study

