3 STUDY FLOW CHART

	Pre-Rx 'Screening Phase' (duration	Baseline	Rx Phase 1		Rx Phase 2		
	= 15 days)	Day 0 +/-7	Day 30 +/-7	Day 90 +/-14	Day 120 +/-14	Day 180 +/-14	Day 360 +/-14
Enrolment Period	1 year						
Medical History**	X	X	X	X	X	X	X
Concomitant Medication(s)	X	X	X	X	X	X	X
Vital Signs	X	X	X	X	X	X	X
Physical Examination	X	X	X	X	X	X	X
ASRS(*)	X	X	X	X	X	X	X
IRLS(*)	X	X	X	X	X	X	X
RLS-QOL(*)		X	X	X	X	X	X
MOS-SS(+*)		X	X	X	X	X	X
CBC and differential, CMP	X		X				X
Monitoring & Recording of Adverse Events		X	X	X	X	X	X
Urine pregnancy analysis	X	X	X	X	X	X	X
Urine sample collection (drug screen)	X						
Serum pregnancy analysis Serum Ferritin Level	TBD	TBD	TBD	TBD	TBD	TBD	TBD

Rx Phase 1 (Day 0-90) = Stable DA + Horizant

Rx Phase 2 (Day 120-360) = DA taper/Horizant only

- + = Subjects will also be requested to keep a sleep diary.
- * = See attachments.
- ** = Medical history includes Interval history between clinic visits.

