Abrupt withdrawal of DA agent can be potentially dangerous due to DA withdrawal symptoms including life-threatening Neuroleptic Malignant Syndrome. Therefore, Rx Phase 1 and Rx Phase are designed to help improve subject tolerability.

Therefore, during Rx Phase 1, Horizant (600 mg oral once daily at 5 pm) will be added on as an adjunct to all subjects' along with stable dose of their current dopaminergic (DA) agent and both medications will be continued for a total period of 90 days from day 0 to day 90.

At the 90th day follow-up visit, with initiation of Rx Phase 2, all subjects will be tapered off (by 50% reduction in dose each week) of their current dopaminergic agent while maintaining the same dose of Horizant and will be on Horizant monotherapy. All subjects will be followed for additional three follow up clinic visits (days 120, 180, 360).

During this period all subjects will be monitored for symptoms of dopamine withdrawal or worsening of RLS or emergence of other symptoms which will be managed clinically by physicians. All subjects will continue to be on Horizant for the entire duration of this study with close follow up. Of note, if deemed appropriate for reasons related to safety, tolerability, and continuation of the study, the PI, at his discretion, may modify the tapering schedule of the DA although every attempt will be made to adhere to the protocol specified schedule of DA tapering.

During each clinic visit all subjects will undergo careful evaluations (by a physician) that will include: medical history such as appearance of any new health problems, any new symptoms/adverse events between clinic visits, concomitant medication(s) history (medication reconciliation), physical examination with assessment of vital signs, ASRS, IRLS, RLS-QOL, and MOS-SS.

All subjects will undergo laboratory testing (CBC with Diff and CMP) during screening, on day 30 and day 360 (final clinic visit). In addition, urine sample will be collected at screen visit for illegal drug testing. Additional hematology and urine sample analysis for illegal drug will be performed as needed at the discretion of the investigators if an adverse event is reported by a subject. Serum Ferritin level will be performed as needed at the discretion of the investigators.

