5. BACKGROUND

5.1 Study Rationale:

RLS is common condition that is usually treated with dopaminergic medications. Augmentation is the main complication during long-term DA treatment of RLS. It was first described in 1996 with overall increase in severity of RLS symptoms typically more severe than pre-dopaminergic therapy with earlier occurrence of symptoms and involvement of previously uninvolved extremities. It can be a very devastating experience in some patients. Augmentation is reported in up to 82% of people taking levodopa (Allen RP, Earley CJ. Augmentation of the restless legs syndrome with carbidopa/levodopa. Sleep 1996;19:205-13)

Features of Augmentation include earlier onset of RLS symptoms, increased severity of symptoms, reduced time before symptoms begin when resting, spread of symptoms to previously uninvolved body parts, and reduced effectiveness of medications including longer time before medication begins to work and less ability to decrease symptoms.

Augmentation severity can be assessed by a validated scale, ASRS, in these patients.

Management of Augmentation has not been studied in clinical trials. Presently, there is no approved medication (by FDA) to treat augmentation. In addition, currently, there are no specific practice guidelines as to how to treat augmentation. 'More research is needed to identify the optimal approach for treating augmentation once it develops. Sudden withdrawal of the offending dopaminergic drug does not appear to be a well-tolerated strategy' (Kurlan. Journal of Parkinsonism & Restless Legs Syndrome Vol 3, 49-52, 2013).

Pubmed search (conducted in Jan 2015, with key words "Horizant, Augmentation") revealed several articles (see attachments) suggesting that Horizant is the only FDA approved Nondopaminergic drug used in the treatment of RLS, with predictable bioavailability, acceptable safety profile and with any reports of augmentation. Therefore, we suggest that Horizant may be a best-suited drug to treat augmentation in RLS patients. Thus, we propose to conduct a clinical drug trial to examine Horizant in RLS patients who developed augmentation.

Abrupt withdrawal of DA agent can be potentially dangerous due to DA withdrawal symptoms including life-threatening Neuroleptic Malignant Syndrome. Therefore, to improve subject tolerability and minimize DA withdrawal, we have designed this clinical trial into 2 phases: Rx Phase 1 and Rx Phase 2 (described below)

6. Objectives:

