8.1 Horizant Stability & Storage

HORIZANT Extended-Release Tablets containing 600 mg of gabapentin enacarbil are white to off-white, with occasional black/grey spots, oval-shaped tablets debossed with "GS LFG". They are supplied as follows:

600 mg: NDC 53451-0101-1: Bottles of 30

Store at 25°C (77°F); excursions permitted 15° to 30°C (59° to 86°F) [see USP Controlled Room

- 8.2 Other Study Drug Generic Name (Brand Name®) Not applicable
- **8.3 Randomization Procedure**: Not Applicable.
- **8.4 Blinding Procedures** Not Applicable
- 8.5 Drug Accountability:

The study site must maintain accurate records demonstrating dates and amount of study drug received, to whom they are dispensed (subject-by-subject accounting), and accounts of any study drug accidentally or deliberately destroyed. If drug is provided by XenoPort, the investigator must return all unused vials of study drug to XenoPort Inc. pursuant to instructions (unless agreed otherwise by XenoPort Inc.).

8.6 Treatment Schedule: as per study design.

8.7 Modification of Treatment Schedule for Horizant:

If deemed necessary for individual subject's safety, it is at the discretion of the treating physician to modify the schedule of dosage of 600 mg according to the approved package insert; however, every attempt should be made to maintain the scheduled study dosing.

8.8 Modification of Treatment Schedule for Other Study Drug: as per protocol.

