11.1.5 Safety Classifications

The following classifications should be considered when evaluating the relationship of adverse events and serious adverse events to investigational drug:

Relationship of Event to Investigational Drug

Not related: Any event that does not follow a reasonable temporal sequence from

administration of investigational drug AND that is likely to have been produced by the subject's clinical state or other modes of therapy administered to the

subject.

Unlikely: Any event that does not follow a reasonable temporal sequence from

administration of investigational drug OR that is likely to have been produced by the subject's clinical state or other modes of therapy administered to the

subject.

Likely: Any reaction that follows a reasonable temporal sequence from administration

of investigational drug OR that follows a known response pattern to the suspected drug AND that could not be reasonably explained by the known characteristics of the subject's clinical state or other modes of therapy

administered to the subject.

Relationship of Event to Investigational Drug

Definitely:

Any reaction that follows a reasonable temporal sequence from administration of investigational drug AND that follows a known response pattern to the suspected drug AND that recurs with re-challenge, AND/OR is improved by stopping the drug or reducing the dose.

Severity of Adverse Events and Serious Adverse Events

The following classifications should be considered when evaluating the severity of adverse events and serious adverse events:

Severity of Event

Mild:

Symptoms(s) barely noticeable to subject or does not make subject uncomfortable; does not influence performance or functioning; prescription drug not ordinarily needed for relief of symptoms(s) but may be given because of personality of subject.

Moderate:

Symptom(s) of a sufficient severity to make subject uncomfortable; performance of daily activity is influenced; subject is able to continue in study; treatment for symptom(s) may be needed.

Severe:

Symptom(s) cause severe discomfort; symptoms cause incapacitation or significant impact on subject's daily life; severity may cause cessation of treatment with investigational drug; treatment for symptom(s) may be given and/or subject hospitalized.

11.2Investigator Responsibilities

The Investigator will:

- Monitor and record all adverse events
- Determine the seriousness, causality, and severity of each adverse event

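### Section 10.2 measures Horizant safety by undivided event occurrence although the protocol itself tapers the dopaminergic agent from Day 90, and no stated item attributes an event to the taper

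*Protocol*

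**What the plan says.** Protocol section 10.2 sets the safety criterion: "The safety and tolerability of Horizant will be determined by the occurrence of and/or Changes in" three things. The first is "Treatment-emergent adverse events"; the others are clinically significant laboratory changes, and new complaints or significant changes on examination. Adverse effects are asked about at every visit. The section gives no time window and no division by phase.

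The protocol changes two exposures. Horizant is added at Day 0. From the Day 90 visit, section 4 states that "all subjects will be tapered off (by 50% reduction in dose each week) of their current dopaminergic agent"; section 6.1 repeats this. Section 5.1 treats DA withdrawal as a hazard in its own right: "Abrupt withdrawal of DA agent can be potentially dangerous due to DA withdrawal symptoms". The two-phase design is justified on that ground.

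The flow chart in section 3 labels the phases "Rx Phase 1 (Day 0-90) = Stable DA + Horizant" and "Rx Phase 2 (Day 120-360) = DA taper/Horizant only". It schedules adverse-event monitoring from Baseline to Day 360.

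On causality, section 11.1.5 states: "The following classifications should be considered when evaluating the relationship of adverse events and serious adverse events to investigational drug". The grades are Not related, Unlikely, Likely and Definitely. Section 8.9 item 1 gives one reason for withdrawing a subject that covers both significant adverse effects after Horizant is added and significant DA-withdrawal effects.

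**The concern.** The criterion in 10.2 is occurrence, not relatedness. A withdrawal symptom that first appears after Day 90 emerges while the subject is taking Horizant and is a new complaint, so on the text of 10.2 it falls within the assessment of Horizant. The causality grade can say that Horizant was not the cause. It cannot say that the taper was, because that question is not asked.

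Two results are at stake. One is the Horizant safety statement, which could carry events that belong to a second, protocol-imposed change. The other is the tolerability of the taper, the step that the protocol itself treats as the delicate one. It would have to be inferred from timing and from events that share the grades Not related or Unlikely with intercurrent illness and every other cause. With one arm and no comparator, nothing else in the design separates the two.

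**Working it through.** The protocol states no adverse-event rate and no safety calculation, so there is no figure to reproduce. The check uses the protocol's own schedule, then an illustration on assumed rates.

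**1. Share of follow-up at or after taper start.** Inputs: last visit Day 360; taper from the Day 90 visit, window ±14 days (section 3).

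- Taper start Day 90: (360 − 90)/360 = 270/360 = 75%.
- Taper start Day 76: (360 − 76)/360 = 284/360 = 79%.
- Taper start Day 104: (360 − 104)/360 = 256/360 = 71%.

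This is calendar time after the taper begins, not time at risk of withdrawal symptoms.

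**2. Where the taper falls.** Halve the dose weekly and count one halving completed per week after Day 90. The remaining DA dose is 0.5^k after k weeks:

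| Day | Remaining DA dose |
|---|---|
| 97 | 50% |
| 104 | 25% |
| 111 | 12.5% |
| 118 | 6.25% |

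About 94% of the scheduled reduction is thus complete by Day 118. The flow-chart labels end Phase 1 at Day 90 and begin Phase 2 at Day 120, so the taper falls in an interval that belongs to neither. Section 4 instead starts Phase 2 at the Day 90 visit. A by-phase table built on the flow-chart labels could leave out the taper itself.

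**3. What is and is not collected.**

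| Provision | Where | Separates taper events? |
|---|---|---|
| Monitoring for dopamine-withdrawal symptoms after Day 90 | 4, 6.1 | Observed, but not listed as an outcome in 10.2 |
| All adverse events recorded whatever the relationship | 11.1.3 | Recorded, with no cause assigned to the taper |
| Causality grade for each event | 11.1.5, 11.2 | Only for or against Horizant |
| Withdrawal of a subject | 8.9 item 1 | No, both causes in one item |

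**4. Illustration of direction only.** The rates are assumed. Let pH be the risk of a Horizant event and pW the risk of a withdrawal event, taken as independent, with n = 50. Undivided incidence = 1 − (1 − pH)(1 − pW). With pH = 20%:

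| pW | Undivided incidence | Subjects of 50 | Added by the taper alone |
|---|---|---|---|
| 0 | 20% | 10 | 0 |
| 10% | 28% | 14 | 4 |
| 30% | 44% | 22 | 12 |
| 50% | 60% | 30 | 20 |

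Over pH = 10% to 30% and pW = 10% to 50%, the taper alone adds between 3.5 and 22.5 expected subjects of 50. The range is wide because nothing in the protocol narrows it, and it applies to an undivided count that ignores the causality grades.

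**The case against.** The strongest reply is that the protocol takes DA withdrawal seriously and that the rest is tabulation. Withdrawal symptoms are monitored in all subjects, are a named reason for leaving the study, and are recorded as adverse events. The investigator must judge causality for each event, and the Not related and Unlikely grades allow other therapy or the clinical state as the cause. Section 10.2 lists what is looked at; it does not say that every event is attributed to Horizant, and it sets no pooled table. The window for treatment-emergent events and a split by phase are ordinary content of a statistical analysis plan, which is not shown here. The CRF is not shown either.

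Most of this stands. A reader might infer that the protocol counts withdrawal harm as Horizant harm, or that harm from the taper is never measured or cannot be reported. The documents support none of these: events are collected visit by visit, the Day 90 visit precedes the taper, and a withdrawal event can be graded Not related. That 10.2 covers the whole study is also an inference, though enquiry at each visit and monitoring to Day 360 point that way. The heading "8.2 Other Study Drug Generic Name", marked not applicable, is weak evidence. It sits with drug supply and storage, and says nothing about how withdrawal events are assessed.

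What the reply does not meet is attribution. An analysis plan can divide a table by date. It cannot supply a judgement about the taper that investigators were not asked to make at the time.

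**Conclusion.** The point holds as a modest, inexpensive improvement. Section 10.2 frames safety as Horizant's alone and does not separate the stable-DA period from the period after the taper. Section 11.1.5 has no item for the taper, and section 8.9 item 1 merges two causes. An undivided event rate from this single arm cannot be read as the rate for Horizant, since 75% of planned days (71% to 79%) fall at or after taper start.

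The size of any distortion is unknown. The illustrative rates rest on assumed, independent risks and show direction only. It would go too far to say that the safety result is wrong, or wrong by a stated factor. Nor should the Horizant statement rest on Days 0 to 90 alone: that would discard the monotherapy period of the secondary objective. Events in those 90 days are also uncontrolled and occur on Horizant combined with a DA, so they are not cleanly attributable to Horizant either.

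**What to change.** - **Section 10.2:** summarise adverse events separately (i) from first Horizant dose to first DA reduction and (ii) from first DA reduction to Day 360. Divide at each subject's actual date of first reduction, because the flow-chart labels leave Days 90 to 120 unassigned, the Day 90 visit has a ±14-day window, and the taper schedule may be modified. In (ii), judge emergence against the state just before the first reduction, and describe the period as Horizant plus DA withdrawal and then monotherapy. Name DA-withdrawal events as a safety outcome. Report both periods.
- **Section 11.1.5 and the CRF:** add one item, relationship to the protocol-specified DA taper, alongside relationship to Horizant.
- **Section 8.9 item 1:** keep the rule, but record which of the two causes applied.
- **Section 3:** reconcile the phase labels with section 4, which starts Phase 2 at the Day 90 visit.

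The cost is one more CRF item, a split reason code and one more table. Each period has fewer days than the whole, about 90 and 270, so estimates within a period are less precise. Because the lengths differ, crude percentages from the two should not be compared without allowing for exposure time. No dose, taper schedule or stopping rule changes.

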11 ADVERSE EVENTS/SERIOUS ADVERSE EVENTS – DEFINITION & REPORTING

At the signing of the informed consent form, each subject will be given the names and telephone numbers of investigational site personnel for reporting adverse events and medical emergencies.

11.1 Definitions

11.1.1 Adverse Event

Any untoward medical occurrence in a patient or clinical investigation subject administered a pharmaceutical product and which does not necessarily have to have a causal relationship with this treatment. An adverse event is any adverse event that is experienced by a subject who has received an investigational drug, but that does not necessarily have a causal relationship with the investigational drug.

11.1.2 Serious Adverse Events

In accordance with 21 Code of Federal Regulations (CFR) Part 312.32 and the recommendations of the International Conference on Harmonization (ICH) [Federal Register, October 7, 1997, Vol. 62, No. 194, pp 52239-45], any of the following adverse events are to be classified as a serious adverse event (SAE):

- An event that results in death.
 - An event that, in the view of the Investigator, places the subject at immediate risk of death (a life-threatening event). This does not include an event that, had it occurred in a more severe form, might have caused death.
 - An outcome that results in a congenital anomaly/birth defect diagnosed in a child of a subject who participated in this study.
 - An event that requires or prolongs in-patient hospitalization.
 - An event that results in persistent or significant disability/incapacity.
 - Other medically important events that, in the opinion of the Investigator, may jeopardize the subject or may require intervention to prevent one of the other outcomes listed in the definition above. (Examples of such medical events include allergic bronchospasm requiring intensive treatment in an emergency room or convulsions occurring at home that do not require an in-patient hospitalization.).

If a serious adverse event is unresolved when a subject permanently discontinues the study, the subject will be followed until the event resolves or the clinical course is stabilized.

11.1.3 Adverse Event Recording/Reporting

All adverse events (including pre-dosing and treatment-emergent) should be recorded in the subject's record (or, if applicable, in the adverse event section of the CRF) regardless of severity or relationship to investigational drug.

11.1.4 Immediate Reporting of Serious Adverse Events

Any SAE required to be reported according to 21 Code of Federal Regulations (CFR) Part 312.32 and the recommendations of the International Conference on Harmonization (ICH) [Federal Register, October 7, 1997, Vol. 62, No. 194, pp 52239-45] that occurs regardless of whether or not the subject has undergone any study-related procedures or received investigational drug, through the completion of trial, will be reported to the FDA. The investigator will forward a copy of the report to XenoPort in the same time frame that it is submitted to the FDA.

The Investigator will notify the local IRB/IEC per local requirements.

11.1.5 Safety Classifications

The following classifications should be considered when evaluating the relationship of adverse events and serious adverse events to investigational drug:

Relationship of Event to Investigational Drug

Not related: Any event that does not follow a reasonable temporal sequence from

administration of investigational drug AND that is likely to have been produced by the subject's clinical state or other modes of therapy administered to the

subject.

Unlikely: Any event that does not follow a reasonable temporal sequence from

administration of investigational drug OR that is likely to have been produced by the subject's clinical state or other modes of therapy administered to the

subject.

Likely: Any reaction that follows a reasonable temporal sequence from administration

of investigational drug OR that follows a known response pattern to the suspected drug AND that could not be reasonably explained by the known characteristics of the subject's clinical state or other modes of therapy

administered to the subject.

Relationship of Event to Investigational Drug

Definitely:

Any reaction that follows a reasonable temporal sequence from administration of investigational drug AND that follows a known response pattern to the suspected drug AND that recurs with re-challenge, AND/OR is improved by stopping the drug or reducing the dose.

Severity of Adverse Events and Serious Adverse Events

The following classifications should be considered when evaluating the severity of adverse events and serious adverse events:

Severity of Event

Mild:

Symptoms(s) barely noticeable to subject or does not make subject uncomfortable; does not influence performance or functioning; prescription drug not ordinarily needed for relief of symptoms(s) but may be given because of personality of subject.

Moderate:

Symptom(s) of a sufficient severity to make subject uncomfortable; performance of daily activity is influenced; subject is able to continue in study; treatment for symptom(s) may be needed.

Severe:

Symptom(s) cause severe discomfort; symptoms cause incapacitation or significant impact on subject's daily life; severity may cause cessation of treatment with investigational drug; treatment for symptom(s) may be given and/or subject hospitalized.

11.2Investigator Responsibilities

The Investigator will:

- Monitor and record all adverse events
- Determine the seriousness, causality, and severity of each adverse event
- Report all serious adverse events to the FDA according to the code of federal regulations
- Forward a copy of all serious adverse events reports sent to the FDA and XenoPort Inc. in the same time frame
- Actively and persistently pursue follow-up of serious adverse events
- Forward a copy of the follow-up information to XenoPort Inc.

11.3Additional Procedures

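### The causality grades in protocol section 11.1.5 overlap, and the ungrouped Likely rule lets the same adverse event be coded in different ways

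*Protocol*

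**What the plan says.** Section 11.1.5 (Safety Classifications) gives four grades for the relationship of an event to the investigational drug.

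- **Not related** joins two conditions with AND: the timing does not fit, and another cause is likely. The key words are: "administration of investigational drug AND that is likely to have been produced by the subject's clinical state or other modes of therapy".
- **Unlikely** uses the same two conditions joined with OR. The key words are: "administration of investigational drug OR that is likely to have been produced by the subject's clinical state or other modes of therapy".
- **Likely** starts with two alternatives, a fitting time course or a known pattern, written as: "of investigational drug OR that follows a known response pattern to the suspected drug". It then adds the clause: "AND that could not be reasonably explained by the known characteristics of the subject's clinical state or other modes of therapy".
- **Definitely** needs both a fitting time course and a known pattern, plus this condition: "AND that recurs with re-challenge, AND/OR is improved by stopping the drug or reducing the dose". It has no condition about other explanations.

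There is no grade between Unlikely and Likely, and no rule for an event that meets more than one definition. Section 11.2 (Investigator Responsibilities) requires the investigator to "Determine the seriousness, causality, and severity of each adverse event".

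The design is single-arm and open-label. According to section 4 (Summary), Horizant is "added on as an adjunct to all subjects' along with stable dose of their current dopaminergic (DA) agent" from day 0 to day 90. The DA is tapered from the day 90 visit.

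**The concern.** A causality scale should give each event exactly one grade. This one has two faults that can be seen in the text.

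First, Not related and Unlikely use the same two conditions, once with AND and once with OR, so anything that satisfies Not related also satisfies Unlikely. Other pairs of grades can also hold together, including pairs on opposite sides of the related/unrelated divide.

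Second, Likely has the form *X or Y and Z* without grouping. The two groupings treat an event with a plausible time course and another possible cause in opposite ways.

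That kind of event can be expected here. All subjects take a second active drug with Horizant in Phase 1, and the taper offers a competing explanation at the start of Phase 2. With no comparator arm, the investigator's attribution is one of the few ways to separate Horizant effects from DA effects. What is at stake is the consistency of that attribution.

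**Working it through.** The protocol states no figure to reproduce. The check is a truth table over the four definitions in section 11.1.5.

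**Attributes**

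- T: reasonable temporal sequence (yes/no).
- K: known response pattern (yes/no).
- Other cause: none; *could* reasonably explain the event; or *likely* produced it. A likely cause is taken to be one that could explain the event.
- D: recurs on re-challenge and/or improves on stopping or reducing (yes/no).

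This gives 2 × 2 × 3 × 2 = 24 profiles.

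**Rules**

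- Not related = (not T) AND other cause likely.
- Unlikely = (not T) OR other cause likely.
- Likely, Reading A = (T OR K) AND no other reasonable explanation.
- Likely, Reading B = T OR (K AND no other reasonable explanation).
- Definitely = T AND K AND D.

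**Grades that each profile meets**

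| T | Other cause | K, D | Profiles | Reading A | Reading B |
|---|---|---|---|---|---|
| no | likely | any | 4 | Not related + Unlikely | Not related + Unlikely |
| no | could | any | 4 | Unlikely | Unlikely |
| no | none | K no | 2 | Unlikely | Unlikely |
| no | none | K yes | 2 | Unlikely + Likely | Unlikely + Likely |
| yes | likely | not both | 3 | Unlikely | Unlikely + Likely |
| yes | likely | both | 1 | Unlikely + Definitely | Unlikely + Likely + Definitely |
| yes | could | not both | 3 | none | Likely |
| yes | could | both | 1 | Definitely | Likely + Definitely |
| yes | none | not both | 3 | Likely | Likely |
| yes | none | both | 1 | Likely + Definitely | Likely + Definitely |

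**Counts**

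- Reading A: no grade 3; more than one grade 4 + 2 + 1 + 1 = 8; exactly one 24 − 3 − 8 = 13.
- Reading B: no grade 0; more than one grade 4 + 2 + 3 + 1 + 1 + 1 = 12; exactly one 24 − 12 = 12.
- On both sides of the divide (Unlikely together with Likely or Definitely): Reading A 2 + 1 = 3; Reading B 2 + 3 + 1 = 6.
- Profiles where another cause could or did likely explain the event: 2 × 8 = 16. Of these, 0 can be Likely under Reading A and 8 (every temporal one) under Reading B.

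The three empty profiles under Reading A are temporal events that another therapy could, but need not, explain and that do not meet Definitely. Reading B rates the same three Likely.

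**The case against.** **The scale is guidance, and little depends on it.** Section 11.1.5 says the classifications are to be considered, which leaves room for clinical judgement. Section 11.1.3 has every adverse event recorded whatever its relationship to the drug. Section 11.2 has all serious adverse events reported. Section 10.2 assesses safety by treatment-emergent events, laboratory changes and new complaints or examination findings, none of them conditioned on a causality grade. Withdrawal under section 8.9 rests on the investigator's judgement. This stands, and it limits the point to attribution. It does not remove the duty in section 11.2 to assign causality to each event, and no other scale is given.

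**The raw counts overstate the conflict.** Under Reading A, 5 of the 8 multiple profiles (4 Not related within Unlikely, 1 Likely with Definitely) could be settled by taking the more specific grade. This also stands, although the protocol states no such rule. The 3 or 6 opposite-side profiles are the better measure. All these counts are logical combinations, not frequencies of real events.

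**A competing DA explanation is not automatic.** Section 7.2 requires at least 6 months on DA and at least 3 months of augmentation on a stable dose, so a new event after Horizant is added need not be put down to the DA. Once the taper is complete, section 4 describes Horizant monotherapy. The argument therefore applies most directly to days 0 to 90 and the taper.

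**A stronger reading is tempting.** A reader might infer that events the DA could explain can never be rated Likely, and that the drug-related rate is therefore understated. The documents do not support this. It holds only under Reading A; under Reading B every temporal event qualifies as Likely, which could push relatedness upward. Even under Reading A, Definitely ignores other explanations and stays open to such events, and the empty profiles do not satisfy Unlikely either. The protocol also defines no drug-related event rate.

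**Conclusion.** The point holds as a drafting defect of minor severity. Under either grouping of the Likely rule, the grades in section 11.1.5 are not mutually exclusive, and some events meet grades on opposite sides of the divide (3 of 24 profiles under Reading A, 6 of 24 under Reading B). For temporal events that the DA or its taper could, but need not, explain, the text gives either no grade (unless Definitely is met) or Likely. Two investigators can therefore differ on the same event while both follow the protocol. The text does not settle which reading is meant, so no direction of bias can be stated.

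The counts assume that a likely cause is also a possible one, and that positive re-challenge or positive de-challenge is each enough for the last condition of Definitely. They give all profiles equal weight and say nothing about how many events would be affected.

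This does not depend on an analysis plan. The definitions are fixed in the protocol and applied as events are assessed, so a later plan could not restore consistent coding.

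**What to change.** Reword section 11.1.5 and the matching CRF field as follows:

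- **Definitely**: as now, and it takes precedence over every other grade.
- **Not related**: no reasonable temporal sequence AND a likely other cause.
- **Unlikely**: exactly one of those two conditions.
- **Possible** (new): reasonable temporal sequence, and the event could be, but is not likely to be, otherwise explained.
- **Likely**: reasonable temporal sequence, and the event is not reasonably otherwise explained.

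The words *but is not likely to be* in Possible are needed. Without them, the 3 profiles with a temporal sequence and a likely other cause that do not meet Definitely would be both Unlikely and Possible.

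Check against the 24 profiles: Not related 4; Unlikely 4 + 2 + 2 + 3 = 11; Possible 3; Likely 3; Definitely 1 + 1 + 1 = 3. The total is 4 + 11 + 3 + 3 + 3 = 24, with exactly one grade each.

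One consequence should be accepted knowingly: a non-temporal, known-pattern event with no other explanation, now both Unlikely and Likely, becomes Unlikely only.

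The cost is wording in one section and the CRF, one added grade, and a possible shift in the number of events labelled drug-related.
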